12.2 Prior and Concomitant Medications

At the first screening visit, subjects will be asked what medications they are taking, as well as those the subject may have taken but discontinued within the 45 days prior to Visit 1. At each study visit, subjects will be asked what concomitant medications they are currently taking or if there have been any changes to their medication since their first visit.

All prior and concomitant ocular and non-ocular medications will be listed using the ITT population including generic name, route of administration, start date, stop date, dosage, and indication. Prior and concomitant medications will be coded using World Health Organization Drug Dictionary Enhanced (WHODD) enhanced version B2, September 2016, to the appropriate Anatomical Therapeutic Chemical (ATC) classification and WHO generic term.

Counts and percentages of ocular and non-ocular concomitant medications will be summarized separately using WHODrug ATC classification and preferred name. Summaries will be displayed by treatment group and for all subjects. Subjects with multiple medications in the same ATC class or preferred name will be counted only once for that respective ATC class or preferred name.

13. Dosing Compliance and Treatment Exposure

13.1 Dosing Compliance

Dosing compliance (% compliance) will be assessed by calculating the number of actual doses received and comparing that to the number of expected doses as follows:

[REDACTED]

The number of actual doses received will be calculated and summarized using the number of dispensed versus returned, used study drug vials. The number of expected doses that will be used for calculating compliance will be calculated as [REDACTED] for all subjects, regardless of study completion status. A categorical compliance variable will also be derived as compliant [REDACTED] and non-compliant [REDACTED].

Treatment compliance (%) will be summarized for the Safety population using continuous descriptive statistics. The compliance categories defined above will be summarized with counts and percentages. A subject listing of compliance will also be produced.

13.2 Treatment Exposure

Extent of exposure will be calculated in days using the following:

[REDACTED] ■ [REDACTED]

Extent of treatment exposure (days) for each subject exposed to study drug will be summarized with continuous descriptive statistics for each treatment group, using the Safety population. A subject listing of treatment exposure will also be produced.

14. Efficacy Analyses

14.1 Primary Analysis

The primary efficacy endpoints are ocular itching assessed at all time points [REDACTED] [REDACTED] and conjunctival redness assessed at all time points [REDACTED] [REDACTED] at Visit 5b and Visit 6. [REDACTED] [REDACTED]. Ocular itching and conjunctival redness will each be analyzed using an [REDACTED] [REDACTED] [REDACTED] Least squares means (LS Means) for each treatment, LS Means treatment differences, and 95% confidence intervals (CIs) for the LS Means treatment differences will be provided.

Multiple imputation employing the MCMC method will be performed for the primary analysis of the primary endpoints using the SAS procedure PROC MI by applying the following SAS code:

[REDACTED]

where

[REDACTED]

After obtaining twenty complete data sets, the following SAS code will be employed to run the model on each data set:

[REDACTED]

where

[REDACTED]

Then, the following SAS code will be used to analyze the combined data:

[REDACTED]

The primary efficacy analyses will be conducted on the ITT population using MCMC multiple imputation methodology for missing data, as described in Section 9.2 and above. Adjustments for multiplicity will not be employed in this exploratory Phase 2 study.

Sensitivity or supportive analyses will be performed on the ITT population, using LOCF and observed data only, as well as on the PP population with observed data only.

Two-sample *t*-tests will be used as additional sensitivity analyses at each post-CAC® time point, as well as non-parametric Wilcoxon rank sum tests for comparing ST266 ophthalmic drops and placebo. Mean treatment differences, 95% CIs for each of the means, and 95% CIs for the mean differences will be presented.

In addition, ANCOVA models will be run separately at Visit 5b and Visit 6 as secondary analyses, with treatment, time point, and time appropriate baseline as covariates for adjustment (accounting for repeated measurements). LS Means for each treatment, the LS Means treatment difference between ST266 ophthalmic drops and placebo, and the corresponding 95% CIs will be calculated from these ANCOVA models. SAS pseudo-code for the ANCOVA model accounting for repeated measures at each Visit follows:

[REDACTED]

An unstructured variance-covariance matrix will be used for the above repeated measures model. If the model does not converge using the unstructured matrix, the first order autoregressive structure and the compound symmetry structure will be employed, in that order.

14.2 Secondary Analyses

The secondary endpoints will be measured at Visits 5b and 6. All secondary endpoints will be assessed pre-CAC and at [REDACTED] post-CAC® [REDACTED]
[REDACTED] at Visits 5b and 6.

Ocular allergic symptoms will be evaluated by the subject and include eyelid swelling [REDACTED]
[REDACTED] and tearing/watery eyes [REDACTED]

Nasal allergic symptoms are also evaluated by the subject and include rhinorrhea, nasal pruritis, ear or palate pruritis, and nasal congestion. Nasal allergic symptoms are collected on a [REDACTED], NOT allowing half unit increments.

A binary nasal composite score of nasal allergic symptoms will be derived for each visit and time point at which nasal allergic symptoms are collected. The nasal composite score will be "Present" if [REDACTED] [REDACTED], and "Absent" if [REDACTED] It will be considered missing if [REDACTED]
[REDACTED]

Ocular allergic signs will be evaluated by the Investigator and include ciliary redness, episcleral redness, and chemosis. Ocular allergic signs are collected on a [REDACTED] scale, [REDACTED]

Analyses will be performed on quantitative secondary endpoints in a manner similar to the primary endpoints for each visit. [REDACTED]
[REDACTED]
[REDACTED]

[REDACTED] The ST266 ophthalmic drops will be compared to placebo at each time point within each visit. The secondary endpoints will be analyzed for the ITT population with observed data only and for the PP population with observed data only.

14.3 Exploratory Analyses

Conjunctival inflammation scores, evaluated by a masked clinician using confocal microscopy post-CAC® [REDACTED] will be measured at Visit 6 in a subset of [REDACTED] subjects at one site. Descriptive statistics will be produced for this exploratory endpoint.

Diary assessments of ocular itching, ocular redness and eyelid swelling will occur for all subjects prior to bedtime and upon awakening from Visit 4b to Visit 6 [REDACTED]
[REDACTED] for all subjects. Two-sample *t*-tests will be used at each diary time point, as well as non-parametric Wilcoxon rank sum tests, for comparing ST266 ophthalmic drops and placebo. In addition to descriptive summary statistics, mean treatment differences, 95% CIs for each of the means, and 95% CIs for the mean differences will be presented.

15. Safety Analyses

The primary safety variable is the incidence of subjects with any adverse event (AE) during the entire study. The secondary safety variables are slit lamp biomicroscopy, dilated fundus examination, VA, and IOP. Safety variables will be summarized as appropriate. All safety analyses will be performed on the Safety population. No statistical inferential testing will be performed for safety variables.

15.1 Adverse Events

An AE is defined as any untoward medical occurrence associated with the use of an investigational product (IP) in humans, whether or not considered IP-related. Treatment-emergent AEs are defined as AEs that occur after the first use of IP. Per the protocol, only AEs that begin or worsen after receipt of the first dose of IP will be captured in the database for this study; therefore, treatment-emergent AEs and AEs are equivalent in this study and will be denoted as AEs. All AEs will be assigned a severity grade of mild, moderate, or severe. Their relationship to IP will be classified as suspected (definite, probable or possible) or not suspected (not related). The expectedness of an AE will be classified as unexpected, expected or not applicable. Documentation of AEs will include onset date, severity, action(s) taken, IP relationship, expectedness, outcome, resolution date, and seriousness. All AEs will be coded using MedDRA classifications with reference to SOCs and PTs (MedDRA version 19.1).

An adverse event is considered serious if, in the view of either the investigator or sponsor, it results in any of the following outcomes:

- Death;
- A life-threatening adverse event;
- Inpatient hospitalization or prolongation of existing hospitalization;
- A persistent or significant incapacity or substantial disruption of the ability to conduct normal life functions;
- A congenital anomaly/birth defect.

Important medical events that may not result in death, be life-threatening, or require hospitalization may be considered serious when, based upon appropriate medical judgment, they may jeopardize the subject and may require medical or surgical intervention to prevent one of the outcomes listed above.

An overall tabular summary of AEs will be presented that includes the number of events and the number and percentage of subjects who experienced at least one event, by treatment group and overall. This summary will also include breakdowns of AEs further categorized as ocular or non-ocular, SAEs, AEs by maximal severity, AEs leading to subject withdrawal and AEs resulting in death. Additional summaries of AEs will be provided showing the number and percentage of subjects who experienced at least one AE, separately for ocular and non-ocular AEs. Ocular and non-ocular AEs will be summarized separately using discrete summary statistics and presented by treatment group at the subject and event level by SOC and PT using the Safety population. If a subject reports the same PT multiple times within the same SOC, that PT will only be reported once within that SOC. As with the PT, if a subject reports multiple conditions within the same SOC, that SOC will only be reported once. The occurrence of AEs suspected to be related to IP will also be tabulated by SOC and PT, separately for ocular and non-ocular events. SAEs will also be summarized separately for ocular and non-ocular events. All AEs will be presented in a listing.

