## 9.2 OTHER STUDY SUPPLIES

The following supplies will be supplied and/or reconstituted by Ora, Inc.:

- Pregnancy tests (Clarity HCG, RAC Medical Boca Raton, FL)
- The allergens used for skin testing and the conjunctival allergen challenge (cat dander, dog dander, cockroach, dust mites, individual species of grasses, individual species of trees, and/or ragweed)
- The ocular anesthetic agent (Fluress) and dilating drops used for the intraocular pressure and dilated fundus examination, respectively
- The ocular anesthetic agent (proparacaine hydrochloride ophthalmic solution) used for the confocal microscopy
- Relief drops

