- Slit Lamp Biomicroscopy: A slit-lamp exam will be performed in both eyes to
  exclude subjects with disallowed ocular conditions (see Appendix 2). Findings
  of abnormality which are not exclusionary should be recorded as Medical
  History.
- Review of Inclusion/Exclusion Criteria: Confirm if subject needs to washout from any current medications and instruct he/she to follow the appropriate washout time periods (refer to Section 10.1.3)
- Titration Conjunctival Allergen Challenge: A conjunctival allergen challenge (CAC) will be performed bilaterally with a perennial allergen (cat dander, dog dander, cockroach, dust mite) that has been serially diluted in buffered saline and administered via a micropipette.

If increasing doses are required (i.e., for insufficient bilateral itching as assessed by the subject and/or redness as evaluated by the Investigator), doses may be skipped. If a positive CAC reaction is not elicited with the first allergen, other allergens to which the subject is sensitized may be used starting at the lowest dose.

Post-CAC Ocular and Nasal Allergic Signs and Symptoms Assessment: Upon completion of the CAC, subjects will receive ocular examination by the Investigator to evaluate all Investigator evaluated efficacy variables and confirm the subject's qualification. Subjects will be asked to assess their ocular and nasal symptoms.

Confidential Page 32 of 81

- IOP Measurement: For subjects eliciting a positive post-CAC reaction, intraocular pressure (IOP) will be measured in each eye by contact tonometry.
- Dilated Fundus Examination: For subjects eliciting a positive post-CAC reaction, a dilated fundus examination will be performed by the Investigator to evaluate the presence or absence of clinically significant fundus abnormalities and vitreous pathology. Findings of abnormality which are not exclusionary should be recorded as Medical History.
- Review of Inclusion/Exclusion Criteria
- Schedule Visit 2a: Qualifying subjects will be scheduled for Visit 2a the following day.

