#### 11 ADVERSE EVENTS

An AE is defined as any untoward medical occurrence associated with the use of an investigational product (IP) in humans, whether or not considered IP-related. An AE can be any unfavorable and unintended sign (eg, an abnormal laboratory finding), symptom, or disease temporally associated with the use of an IP, without any judgment about causality. An AE can arise from any use of the IP (eg, off-label use, use in combination with another drug or medical device) and from any route of administration, formulation, or dose, including an overdose.

All AEs spontaneously reported by the subject and/or in response to an open question from study personnel or revealed by observation, physical examination or other diagnostic procedures will be recorded in the source document and on the appropriate pages of the eCRF. Any clinically relevant deterioration in clinical finding is considered an AE and must be recorded. When possible, signs and symptoms indicating a common underlying pathology should be noted as one (1) comprehensive event. Any pre-existing medical condition that worsens after administration of study medication will also be considered an adverse event. Study medication includes the drug under evaluation or any other medications required by the protocol given during any stage of the study.

Ocular complaints should not be addressed as AEs unless the complaint is outside the normal limits for allergic conjunctivitis symptoms after allergen exposure or is associated with clinical sequelae (i.e., adverse slit lamp examination finding).

Documentation regarding the AE should be made as to the nature, date of onset, end date, severity, relationship to IP, action(s) taken, seriousness, and outcome of any sign or symptom observed by the physician or reported by the subject upon indirect questioning.

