15.4 Dilated Fundus Examination

Dilated fundus examinations will be performed at Visits 1 (post-CAC®) and 6 (post-CAC®). Counts and percentages of normal and abnormal results will be presented for both eyes combined by visit and treatment group for the following regions: vitreous, retina, macula, choroid, and optic nerve. A change from baseline will also be summarized as follows: [REDACTED]

[REDACTED] Results will be listed for both eyes at each visit.

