15.5 Intraocular Pressure (IOP)

IOP will be measured at Visits 1 (post-CAC®) and 6 (post-CAC®). IOP will be summarized for both eyes combined by visit and treatment group using quantitative summary statistics. At Visit 6, an IOP of [REDACTED] AND [REDACTED] will be considered an Adverse Event, and presented in the tabular summary. IOP will be listed for both eyes at each visit.

16. Interim Analyses

No interim analyses are planned for this study.

17. Changes from Protocol-Stated Analyses

There are no changes from the protocol-stated analyses.

18. References

Not applicable

19. Revision History

Documentation of revision to the SAP will commence after approval of the Final version 1.0.

20. Tables

Tables that will be included in the topline delivery are shown in boldface font.

21. Listings

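### Does SAP 15.1 need a treatment-emergent flag because the protocol's study-medication wording reaches drops given before the first dose?

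*SAP*

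**What the plan says.** SAP 15.1 defines a treatment-emergent AE as one that occurs after the first use of IP. It then gives its reason for not carrying a separate category: "Per the protocol, only AEs that begin or worsen after receipt of the first dose of IP will be captured in the database", and therefore "treatment-emergent AEs and AEs are equivalent in this study and will be denoted as AEs". SAP 15 makes the incidence of subjects with any AE over the whole study the primary safety variable. Safety is analysed on the Safety population without inferential tests.

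Protocol 11 ties its basic AE definition to use of an IP. It then adds: "Any pre-existing medical condition that worsens after administration of study medication will also be considered an adverse event". The term study medication is wide: "Study medication includes the drug under evaluation or any other medications required by the protocol given during any stage of the study".

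Protocol 9.2 lists among the supplies "The ocular anesthetic agent (Fluress) and dilating drops used for the intraocular pressure and dilated fundus examination, respectively". Protocol 10.3.2 places both examinations at Visit 1: "For subjects eliciting a positive post-CAC reaction, intraocular pressure (IOP) will be measured in each eye by contact tonometry", with the dilated fundus examination under the same condition. SAP 15.4 and 15.5 give the same timing. Visit 1 is Day -2, and the first IP drop is at Visit 3, Day 1.

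**The concern.** The SAP drops the distinction between AEs and treatment-emergent AEs on the strength of a rule it attributes to the protocol, and that rule cannot be found in the readable protocol. Meanwhile the wide definition of study medication in Protocol 11 covers drops that every enrolled subject should receive two days before IP, since only subjects with a positive challenge reaction continue. Protocol 11 sends all AEs to the eCRF.

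If a site followed that sentence to the letter, a worsening between Visit 1 and the first dose could be entered as an AE. It would then be counted as treatment-emergent, because the tables apply no onset filter. Day 1 adds a difficulty: the baseline challenge and the first dose fall on the same day, and the AE items listed in Protocol 11 and SAP 15.1 include an onset date but no time. At stake is whether the main safety table counts only events that followed IP.

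**Working it through.** The plan states no figure to reproduce, so the check is mainly a comparison of passages.

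**1. Is there a literal path for a pre-dose AE?** Yes, a narrow one. The study-medication sentence in Protocol 11, the supplies in Protocol 9.2 and the Visit 1 procedures in Protocol 10.3.2 together allow a pre-existing condition that worsens after the Visit 1 drops to be called an AE. Protocol 11.1.2 also lists absence of IP exposure among the grounds for classing an AE as not related, so the causality scale contemplates such a case.

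**2. What do sites actually do before the first dose?** The visit procedures send pre-dose findings elsewhere.
- Visit 1 (Protocol 10.3.2): slit-lamp and fundus abnormalities that are not exclusionary are recorded as medical history.
- Visits 2a, 2b and 3 (Protocol 10.3.3 to 10.3.5): each opens with an update of medical and medication history.
- AE query: none is listed at Visits 1, 2a or 2b. The first is at Visit 3, after IP is dispensed.
- Visual acuity: a clinically significant decrease is called an AE only from Visit 4a.

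This is the collection rule that SAP 15.1 describes.

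**3. Do serious events open a second path?** Protocol 11.3.2 requires all serious events to be reported regardless of relationship to IP. That phrase concerns causality, not timing. Protocol 11.2 defines a serious event as a kind of AE, so it inherits the IP-linked definition. The section gives no start time, but it does not tell sites to record pre-dose events.

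**4. What would happen to a stray pre-dose record?** SAP 15.1 already says what treatment-emergent means, and SAP 1 says the SAP's methods supersede the protocol's. SAP 15.1 includes the onset date among the AE items, and all AEs are listed. A Day -2 or Day -1 onset can therefore be identified from the date alone. Only a Day 1 event could be ambiguous, and whether the eCRF resolves it cannot be judged because the eCRF is not shown.

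**5. How much could one record matter?** Take one subject whose only AE was pre-dose, with about 70 enrolled (Protocol 7.1). The allocation ratio is redacted, so the per-arm figures are assumptions.

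| Denominator | Formula | Shift in AE incidence |
|---|---|---|
| All subjects | 1/70 | 1.4 points |
| One arm, 1:1 assumed | 1/35 | 2.9 points |
| Larger arm, 2:1 assumed (70 × 2/3 ≈ 47) | 1/47 | 2.1 points |
| Smaller arm, 2:1 assumed (70 × 1/3 ≈ 23) | 1/23 | 4.3 points |

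These are the weights of any single subject, not an estimate of how many would be misclassed. To count at all, a pre-existing condition would have to worsen after the Visit 1 drops and be entered as an AE instead of history. The subject would also have to pass the eligibility reviews and slit-lamp examinations at Visits 2a, 2b and 3, and then be dosed. Ordinary reactions to allergen exposure are excluded, because Protocol 11 does not treat them as AEs.

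**The case for a change.** The best argument for a change is that the SAP rests on a premise it does not support. The readable protocol never limits AE capture to the period after first dose. It says at the end of 10.3.10 that AEs are monitored throughout the study, and its causality scale allows for an AE without IP exposure. A spontaneous report before dosing needs no scheduled query to reach the eCRF. A derived flag would be cheap and would make the table right whichever reading a site took.

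Part of this stands. The study-medication sentence is wider than the SAP's rule, and the two do not fit neatly. But the premise is unsupported by the readable text, not shown to be false. Protocol 12.6 (safety analysis) appears in the table of contents while its text is withheld. The SAP cites protocol version 2.0, and the document supplied is version 3.0. The capture rule may sit in either place, and withheld text cannot be taken as absent. The flag would also add little to what the SAP's own definition and the onset date already provide.

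**Conclusion.** No change is needed. There is a loose fit between one broad sentence in Protocol 11 and the capture rule in SAP 15.1. The visit procedures follow the SAP rule, and the SAP's existing definition tells an analyst how to treat an exception. No pre-dose AE is shown to reach the database. If one did, it would shift a descriptive incidence by 1.4 points overall, or by 2.1 to 4.3 points in one arm under the assumed ratios. Pre-dose events are not expected to favour either arm, no safety test depends on the count, and the efficacy conclusions are untouched.

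This rests on three assumptions: sites record pre-dose findings as the visit procedures direct, the Safety population (definition redacted) is made up of dosed subjects, and the analyst checks onset dates against first dose before producing the tables.
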